2 INTRODUCTION

2.1 STUDY RATIONALE

Since December 2019, SARS-CoV-2 (SARS-CoV-2; COVID-19) infections are over 6 million persons and approaching 200,000 deaths in the US with a continually rising rate of infection. Of the ≈20% of patients admitted to hospital, up to half progress to ICU admission, respiratory failure or death. Prominent among these progressors are older men, particularly those with underlying comorbidities (e.g., hypertension, diabetes, lung, heart, kidney or liver disease, obesity and immunocompromised)¹, all common among Veterans. Effective interventions are few, other than recently-approved remdesivir, which shortened hospital stay but did not decrease overall mortality¹⁶. Convalescent plasma from persons recovered from SARS-CoV-2 infection is readily available for treatment.

Convalescent plasma therapy is being used empirically, although only five of six small uncontrolled case series (total n=56) in SARS-CoV-2³⁻⁸ and a recent study with non-randomized controls⁹ suggest improved selected clinical, virologic and laboratory outcomes and outcomes in another small randomized trial were equivocal¹⁷. For other infections, such as influenza and Ebola virus, promising observational studies were not reliably confirmed by controlled trials^{10,11-15}. In multiple infections, use of convalescent plasma has been distinguished by its safety profile but not by the consistency of its benefit. The current double-blind, placebo-controlled RCT is designed to determine definitively whether this intervention is effective in a population at high risk of complications and death from SARS-CoV-2 infection. We compare the effect of convalescent plasma vs. saline placebo with a robust study design, adequate sample size and statistical and logistical rigor to assure that the interventions we make to treat serious disease are well-validated to support its use or to move on to test other potentially safe and effective treatments.

2.2 BACKGROUND

Purpose of the Study

The newly emergent coronavirus SARS-CoV-2 has exceeded two earlier highly fatal species—severe acute respiratory syndrome coronavirus (SARS-CoV) in 2003 and Middle East respiratory syndrome coronavirus (MERS) in 2012 in the speed and breadth of its transmission worldwide and four common upper respiratory coronavirus species in its virulence and associated mortality. Described initially in Wuhan, China, the infection has already spread to infect over 25 million persons worldwide with 860,000 deaths as of September 1, 2020, and over 6 million infected in the U.S. and approaching 200,000 deaths. Although the majority of persons infected recover naturally based on their own innate and adaptive immune responses, up to 20% are ultimately hospitalized with an increased risk of respiratory failure and death. Persons age 65 years or older represent a minority of infections but comprise the majority of those with complications, hospitalization and death^{1,18}. These outcomes are most prominent among older persons with comorbidities, e.g., chronic lung, cardiac and renal disease, as well

as hypertension, diabetes, obesity and immunosuppression¹⁻², conditions common among veterans.

In the absence of an effective vaccine or other biologic preventive measures, treatment options for those with serious disease are also limited. To date, only one antiviral medication (remdesivir) has shown efficacy to shorten time to recovery but not decrease mortality¹⁶. Multiple medications to limit viral replication, minimize inflammation, modulate immune responses are in broad empiric use and testing¹⁹, but none other has been proven to be effective²⁰⁻²³ and a number have untoward side effects²².

Convalescent plasma from persons recovered from SARS-CoV-2 is being used to treat hospitalized individuals with complicated COVID-19 infection. Although relatively safe and widely used, only sparse data support the efficacy of this intervention to limit respiratory failure and death. With other infections (SARS, influenza, Ebola), initiation of plasma therapy early in hospitalization was variably associated with improved outcomes^{14,24,25}, outcomes that may not be consistently confirmed in randomized controlled trials^{26,27}. Validating the efficacy of convalescent plasma therapy for COVID-19 is an important goal, given the contradiction between results of ad hoc versus controlled evaluations of convalescent plasma for other acute viral infections. We will determine the ability of convalescent plasma initiated early in the course of hospitalized disease to decrease respiratory failure and death from SARS-CoV-2 with a robust prospective, randomized, placebo-controlled study protocol. In the context of an acute threatening pandemic, we are compelled to intervene; we propose to determine whether we are using an effective intervention and doing no harm.

Study Design

The parent VA CURES study is an adaptive set of randomized double-blind placebo-controlled trials to evaluate the safety and efficacy of novel therapeutic agents in hospitalized adults diagnosed with COVID-19; VA CURES-1 determines the impact of convalescent plasma vs. saline on critical clinical outcomes. The study is a multicenter trial that will be conducted at VA Medical Centers to compare different investigational therapeutic agents to a control arm. New arms can be introduced according to scientific and public health needs. There will be interim monitoring to allow early stopping for futility, efficacy, or safety. If one therapy proves to be efficacious, then this treatment may become the control arm for comparison(s) with new experimental treatment(s). Any such change would be accompanied by an updated sample size. This adaptive platform is used to rapidly evaluate different therapeutics in a population of those hospitalized with moderate to severe COVID-19. The platform will provide a common framework sharing a similar population, design, endpoints, and safety oversight. New stages with new therapeutics can be introduced and will be described in a stage-specific appendix. One independent Data and Monitoring Committee (DMC) will actively monitor interim data in all stages to make recommendations about early study closure or changes to study arms.

This adaptive design clinical trial may involve multiple stages each investigating different interventions. In order to clearly convey the protocol elements, interventions, objectives and endpoints for each stage, common elements are described in the main protocol document while each stage is noted in a stage-specific appendix.

The first stage in the clinical trial is:

Stage 1: Convalescent Plasma vs Saline (VA CURES-1)

If convalescent plasma is shown to be beneficial in Stage 1, we may proceed to the next stage (Stage 1a) under separate review and protocol:

Stage 1a: Convalescent Plasma vs Fresh Frozen Plasma (VA CURES-1a)

Participants will be assessed daily while hospitalized with a series of efficacy, safety, and laboratory assessments. See stage-specific schedule of assessments for details.

2.3.2 KNOWN POTENTIAL BENEFITS

The possibility that use of convalescent immune plasma may be associated with benefits is supported by a limited number of small case series^{3,5-7} and a non-randomized controlled study with SARS-CoV-2⁹, and few prospective randomized trials with SARS-CoV²⁴, MERS^{25,31}. These benefits have included decreased oxygen requirement, improved pulmonary infiltrates, decreased duration of hospitalization, more rapid resolution of viral detection, improvement in inflammatory laboratory parameters and, in some cases, mortality^{3,24,32}. More substantial results support the use of convalescent plasma with influenza with decreased mortality and length of hospital stay^{10,25,33}, particularly in very early studies and when administered earlier in the course of disease and hospitalization (≤ 4 days for influenza).

Mechanistically, the potency of convalescent plasma is thought to be due to neutralizing antibodies, particularly to the surface S spike and receptor binding domain of the virus³⁴ that prevent binding to epithelial and other target cells as well as cell-to-cell spread. However, antibodies may also enhance virulence mechanisms as well as neutralize³⁵⁻³⁷. Antibodies in convalescent plasma may facilitate clearance of bacterial and viral coinfections and modify inflammation and modulate T cell function³⁸, limit neutrophil adhesion to and activation of endothelial cells and support antigen-presentation to facilitate immune responses.

It is also possible that non-convalescent plasma would have some benefit. Polyclonal antibodies in plasma likely avoid selection of viral escape mutants that can accompany therapy with monoclonal antibodies. Non-neutralizing antibodies may serve a range of Fc-mediated protective effects^{39,40} by supporting antibody-dependent cellular cytotoxicity (ADCC) by natural killer (NK) and cytotoxic lymphocytes to kill infected cells and supporting phagocytosis of virus and infected cells (ADCP). Non-antibody protective functions of plasma may mediate inhibition of inflammation and cytokine production and regulate complement-dependent lung epithelial and vascular endothelial damage⁴¹ with regulatory proteins such as CD55⁴². The volume of plasma infused is unlikely to modify clotting parameters.

2.3.3 ASSESSMENT OF POTENTIAL RISKS AND BENEFITS

The safety of fresh frozen plasma, including convalescent immune plasma from persons with SARS-CoV-2, given to persons with active disease is high. The potential benefits, as above, include decreased mortality, decreased hospital length of stay and improvement in hypoxemia, pulmonary infiltrates and overall clinical status by a range of mechanisms. All of these outcomes are based on very sparse case series and almost all studies are of low or very low quality, lacked controls groups, and were at moderate to high risk of bias²⁵. Hence, we believe that equipoise about the risks and benefits exist. A prospective randomized placebo-controlled study provides credible and actionable results to support or negate the use of this intervention. The results also provide a solid rationale for more selective and effective interventions with antibody alone (purified polyclonal or monoclonal), non-immune plasma alone, or specific plasma components that may be more readily accessible and affordable to persons within the VA and worldwide.

3 OBJECTIVES AND ENDPOINTS

Table 2. Objectives and Endpoints.

OBJECTIVES	ENDPOINTS (OUTCOME MEASURES)
Primary	
To evaluate the clinical efficacy of different investigational therapeutics as compared to the control arm as assessed by: 
 • Proportion of patients who died from any cause or had respiratory failure by Day 28 	
 • Died from any cause; • Respiratory failure is defined by requiring mechanical ventilation, with or without endotracheal intubations, or extra-corporeal membrane oxygenation. 
This is evaluated up to and including Day 28.

Key Secondary	
To evaluate the clinical efficacy of different investigational therapeutics as compared to the control arm, as assessed by: 
 • Time (in days) to recovery (as defined by attaining stages 1, 2 or 3 on the WHO 8-point ordinal scale) 	
Day of recovery is defined as the first day on which the subject satisfies one of the following three categories from the WHO ordinal scale:
 
 • Hospitalized, not requiring supplemental oxygen; • Not hospitalized, limitation on activities and/or requiring home oxygen; • Not hospitalized, no limitations on activities. 
This is evaluated up to and including Day 28.

Additional Secondary	
1. To evaluate the clinical efficacy of different investigational therapeutics as compared to the control arm as assessed by: 
 • Time (in days) to death or respiratory failure by Day 28 	
Time to death or respiratory failure is defined as the first day on which the subject died from any cause or had respiratory failure (defined above).
 
This is evaluated up to and including Day 28.

2. To evaluate the clinical efficacy of different investigational therapeutics as compared to the control arm as assessed by: 
 • Proportion of patients who died from any cause, had respiratory failure or required humidified heated high-flow nasal cannula (HFFNC) at ≥ 15 Lpm by Day 28 • Time (in days) to death or respiratory failure or HFFNC at ≥ 15 Lpm by Day 28 	
This is evaluated up to and including Day 28.


3. To evaluate the clinical efficacy of different investigational therapeutics as compared to the control arm as assessed by:
 
 • Mortality 
 o 28-day all-cause mortality 	
 • Date and cause of death (if applicable)

 • Clinical Severity 
 1) 8-point ordinal scale: (WHO) 
 ▪ Time to an improvement of one category from Day 1 (baseline) using the WHO ordinal scale. ▪ Time to an improvement of two categories from Day 1 (baseline) using the WHO ordinal scale. ▪ Subject clinical status using ordinal scale at Days 2, 4, 7, 11, 14, 21, and 28. ▪ Mean change in the WHO ordinal scale from Day 1 (baseline) to Days 2, 4, 7, 11, 14, 21, and 28. 	
 • WHO ordinal scale (See Table 3) 
Clinical outcome assessed using ordinal scale daily while hospitalized and on Days 14, 21, and 28.

 2) National Early Warning Score (NEWS2)^{43,44}: 
 ▪ Time to discharge from initial hospitalization or to a NEWS2 of ≤ 2 and maintained for 24 hours, whichever occurs first. ▪ Change from Day 1 (baseline) to Days 2, 4, 7, 11, 15, and 29 in NEWS2. 	
 • NEWS2 assessed daily while hospitalized and on Days 15 and 29 (if the participant attends an in-person visit or still hospitalized)

 • Hospitalization 
 ▪ Duration of initial hospitalization (days). ▪ Number of hospitalizations related to COVID-19 	
 • Number and days of hospitalizations up to and including Day 28


4. To evaluate the safety of different investigational therapeutics as compared to the control arm as assessed by:
 
 • Cumulative incidence of SAEs through Day 29. • Cumulative incidence of Grade 3 and 4 clinical and/or laboratory AEs through Day 29. • Discontinuation or temporary suspension of study product administrations (for any reason) • Changes in complete blood count with differential, hemoglobin, platelets, creatinine, glucose, total bilirubin, alanine aminotransferase (ALT), aspartate aminotransferase (AST), and prothrombin time (PT) reported as international normalized ratio (INR) over time (analysis of lab values in addition to AEs noted above). 	
 • SAEs • Grade 3 and 4 AEs • Change in total WBC number, neutrophil number, lymphocyte number, hemoglobin, platelets, creatinine, glucose, total bilirubin, ALT, AST, and PT/INR from Day 1 to Days 2, 4, and 7 (while hospitalized); and Days 15 and 29 (if attends in-person visit or still hospitalized).
Exploratory	

1. To examine if the effect of convalescent plasma is associated with the days of symptoms at time of plasma administration
	
 • Plasma administered on day ≤ 7 vs. >7 days of symptoms on primary outcome

2. To examine if effect of convalescent plasma differs by comorbidities
	
 • Primary outcome in persons with ≤ 2 or ≥ 3 comorbidities (age ≥ 65 years, chronic lung, cardiac and renal disease, hypertension, diabetes, obesity and immunosuppression)

3. Research sample collection and management for future investigations:
 
Respiratory samples on days 1, 4, 7, 15, 29 and 30 mL of blood on days 1, 2, 4, 7 in hospital and days 15 and 29 in- or outpatient.
	
 • Sample Collection (Research lab draw with routine labs), preparation, labeling, shipping, storage and monitoring will be addressed in a future amendment.

4. Impact of donor convalescent plasma parameters on the activity of administered plasma
	
 • Donor plasma samples retained by Vitalant Blood services and provided to CURES-1 investigators will be tested for antibody levels, neutralization against SARS-CoV2, inflammatory and other mediators in relation to clinical and laboratory outcomes in study subjects.

World Health Organization (WHO) Ordinal Scale

WHO 8-point ordinal scale for clinical improvement, modified for use in this study, is described in **Table 3**. Note that this scale is being calculated to permit comparability of VA CURES-1 to other studies of experimental therapies for COVID-19, although a clinical score of “5” by the WHO scale differs from the operational definition of acute hypoxic respiratory failure for use in determining this study’s primary outcome.

Table 3. Modified WHO 8-point Ordinal Scale for Clinical Improvement

Patient State	Descriptor	Clinical Score
Uninfected	No clinical or Virologic evidence of infection	0
Ambulatory	No limitation of activity	1
	Limitation of activity and/or home oxygen	2
Hospitalized Mild disease	Hospitalized, no oxygen therapy	3
	Oxygen by mask or nasal prong	4
Hospitalized Severe disease	Humidified high-flow oxygen	5a
	Non-invasive ventilation	5b
	Intubation and mechanical Ventilation	6
	Ventilation + additional organ support— pressors, RRT, ECMO	7
Dead	Death	8

National Early Warning Score-2

NEWS2 has demonstrated an ability to discriminate subjects at risk of poor outcomes⁴³. This score is based on seven clinical parameters (see **Table 4**). The NEWS2 is being used as an efficacy measure. The NEWS2 Score should be evaluated daily while hospitalized and on Days 15 and 29. It can be performed concurrently with the Ordinal Scale. NEWS2 should be evaluated at a consistent time for each applicable study day, if possible. The seven parameters can be obtained from the hospital chart or electronic medical record (EMR) using the last measurement prior to the time of assessment. A numeric score is given for each parameter (e.g., a RR of 9 is one point, oxygen saturation of 92 is two points). This value is recorded for the day obtained (i.e., on Day 3, the vital signs and other parameters from Day 3 are used to obtain NEWS2 Score for Day 3). ECMO and mechanically ventilated subjects should be assigned a score of 3 for RR (RR <8) regardless of the ventilator setting. Subjects on ECMO should get a score of 3 for heart rate since they are on cardiopulmonary bypass.

Table 4. The NEWS Scoring System⁴³

Physiological parameter	Score						
	3	2	1	0	1	2	3
Respiration rate (per minute)	≤ 8		9-11	12-20		21-24	≥ 25
SpO ₂ Scale 1 (%)	≤ 91	92-93	94-95	≥ 96			
SpO ₂ Scale 2 ¹ (%)	≤ 83	84-85	86-87	88-92 ≥ 93 on air	93-94 on oxygen	95-96 on oxygen	≥ 97 on oxygen
Air or oxygen?		Oxygen		Air			
Systolic blood pressure (mmHg)	≤ 90	91-100	101-110	111-219			≥ 220
Pulse (per minute)	≤ 40		41-50	51-90	91-110	111-130	≥ 131
Consciousness ²				Alert			CVPU
Temperature (C)	≤ 35.0		35.1-36.0	36.1-38.0	38.1-39.0	≥ 39.1	

¹SpO₂ Scale 2 is used only for participants with history of pre-existing suspected or confirmed hypercapnia.

²Level of consciousness = alert (A), conscious but non-alert (C) and arousable only to voice (V) or pain (P), or unresponsive (U).

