8.2 BASELINE, RANDOMIZATION AND PRODUCT ADMINISTRATION

Baseline assessments should be performed before the first study product administration.

The following eligibility/baseline assessments can be done up to 72 hours prior to randomization time: demographic information (age, ethnicity, gender, body mass index), medical history/baseline comorbidities (e.g. obesity, smoking, diabetes, hypertension, cardiac, renal, liver, and lung disease), and physical exam.

Baseline clinical status data are collected right before randomization. Baseline vital signs (NEWS2) should be collected closest to randomization time and must be collected within 24 hours prior to randomization time.

The following additional baseline assessments are collected prior to study product administration:

- COVID-19 signs and symptoms, including day of onset,
- Medications for this current illness taken in the 7 days prior to Day 1 (See Section 6.5),
- Designated pre-admission medications by class (See Section 6.5),
- Adverse events (See Section 8.5),
- Safety and research labs (See Section 8.4).

Day 1 safety and research labs should be collected up to 24 hours prior to randomization and before first study product administration. Laboratory tests performed as part of routine clinical care within the same time period will be accepted for Day 1 safety laboratory tests.

Ideally, product administration should start on the same day as randomization (Day 1), but may be started up to 36 hours after randomization.

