8.3.3 NATIONAL EARLY WARNING SCORE 2 (NEWS2)

The NEWS2 point score (<https://www.mdcalc.com/national-early-warning-score-news-2>)⁴³ will be used (see **Table 4, Section 3, Objectives and Endpoints**):

- 1) to assess the severity of illness and comparability of subjects in the convalescent plasma and control groups at enrollment, and
- 2) to compare changes in score over time between the two groups. Patients who die will be coded on their values on the day of death if the values are available.

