2.2 SAMPLE SIZE DETERMINATION

Primary endpoint

The Chi-square test will be used to compare treatment arms on the proportion of death from any cause or respiratory failure up to and including Day 28, with two-sided significance level = 0.05.

A meta-analysis of studies of SARS coronavirus infection and severe influenza reported that convalescent plasma led to an absolute reduction in the risk of mortality from 7% to 23% and a 54% greater likelihood of discharge by day 22²⁵. These data suggest that the treatment benefit of convalescent plasma in reducing the risk of death and respiratory failure may be substantial, particularly early in hospitalization. For this trial we conservatively assume a 10% absolute reduction (30% in the control group and 20% in the convalescent plasma group) given that this trial allows local standard of care in both arms, which may include effective medications for COVID-19.

Table 6. Required number of participants to have 80%, 85% or 90% power for the primary outcome, assuming no missing data.

Proportion in the control group	Absolute reduction	Corresponding proportion in the plasma group	Number of participants needed		
			80% power	85% power	90% power
35%	11%	24%	532	610	712
	10%	25%	652	746	874
	9%	26%	858	976	1134
	8%	27%	1042	1192	1396
30%	11%	19%	474	542	634
	10%	20%	582	666	778
	9%	21%	730	834	976
	8%	22%	936	1072	1254
25%	11%	14%	400	458	536
	10%	15%	496	566	662
	9%	16%	624	714	836
	8%	17%	806	922	1080

Table 6 provides the total number of participants needed for 80%, 85% or 90% power to detect a range of differences in the primary outcome, using the z-test with a two-sided significance level = 0.05 and assuming no missing data. A total of 666 participants are needed to have 85% power for a 10% absolute reduction when the proportion of death or respiratory failure is 30% in the control group (**Table 6**). This sample size has 76% power to detect a 9% absolute reduction

when the control rate is 30% and has 90% (81%) power to detect a 10% absolute reduction when the control rate is 25% (35%) (**Table 7**).

Table 7. Power of a study of 666 participants to detect differences in the primary outcome, assuming no missing data.

Proportion in the control group	Absolute reduction	Corresponding proportion in the convalescent plasma group	Power
35%	11%	24%	88%
	10%	25%	81%
	9%	26%	72%
	8%	27%	61%
30%	11%	19%	91%
	10%	20%	85%
	9%	21%	76%
	8%	22%	66%
25%	11%	14%	95%
	10%	15%	90%
	9%	16%	83%
	8%	17%	72%

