2.4 STATISTICAL ANALYSES

2.4.1 GENERAL APPROACH

This is a double-blind controlled randomized trial testing a superiority hypothesis of convalescent plasma versus saline with a two-sided type I error rate of 5%. Secondary hypotheses have been ordered according to relative importance, with one key secondary hypothesis highlighted. These will be described according to the appropriate summary statistics (e.g., proportions for categorical data, means with 95% confidence intervals for continuous data, median for time-to-event data).

A statistical analysis plan will be developed prior to unblinding of study and database lock.

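### No model using the Day 1 value as a covariate is stated for NEWS2 and safety laboratory change, so the plan read literally gives an unadjusted change comparison

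*Combined protocol and SAP*

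**What the plan says.** Table 2 (Section 3) lists, among the additional secondary efficacy endpoints, "Change from Day 1 (baseline) to Days 2, 4, 7, 11, 15, and 29 in NEWS2". Section 8.3.3 gives this a between-arm purpose: "to compare changes in score over time between the two groups". For safety, Table 2 lists "Change in total WBC number, neutrophil number, lymphocyte number, hemoglobin, platelets, creatinine, glucose" and the remaining laboratory tests, again from Day 1, under an objective framed as a comparison with the control arm.

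For analysis, Section 9.4.1 (printed as 2.4.1) offers "means with 95% confidence intervals for continuous data" as an example of a suitable summary. The numbered list of other secondary analyses in Section 9.4.3 covers binary, ordinal, time-to-event, duration and categorical data; it has no item for continuous change. Section 9.4.4 tests only proportions of participants with adverse events. Covariate adjustment is planned for the primary endpoint (9.4.2) and for time to recovery (9.4.3), but neither covariate list contains baseline NEWS2 or a baseline laboratory value.

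The Day 1 measurements needed are already required. Section 8.2 says that baseline NEWS2 "must be collected within 24 hours prior to randomization time", and it schedules Day 1 safety laboratory tests before the first infusion. Section 9.4.1 also states: "A statistical analysis plan will be developed prior to unblinding of study and database lock".

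**The concern.** A raw change score subtracts the whole Day 1 value, as if each extra point on Day 1 predicted exactly one extra point at follow-up. When the true slope differs from one, the subtraction leaves avoidable noise in the comparison. A model with Day 1 as a covariate estimates that slope from the data. With equal SDs and a correlation below 0.5, raw change is even noisier than ignoring baseline altogether. A low correlation is plausible for NEWS2 at Days 15 and 29, well after an acute admission, and less obviously so at Days 2, 4 and 7.

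What is at stake is the precision of the between-arm estimates for one listed efficacy measure and for the laboratory safety measures. With six NEWS2 time points and no named model, the choice between adjusted and unadjusted analysis also stays open.

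**Working it through.** **Inputs from the documents.** Both endpoints are changes from Day 1 (Table 2). Allocation is 1:1 (Section 6.3.1). The documents give no SD, correlation, target effect or power for NEWS2 or any laboratory value, so rho (the correlation of Day 1 with follow-up) and k (follow-up SD divided by Day 1 SD) below are assumptions, shown over a range.

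**The plan's own sample size.** It concerns the binary primary endpoint only, 30% vs 20% with 85% power, "with two-sided significance level = 0.05" (Section 9.2). The unpooled z-test gives (0.30×0.70 + 0.20×0.80)×(1.960 + 1.036)² / 0.10² = 0.37×8.98/0.01 ≈ 332.2, so 333 per arm and 666 in total. Dividing by 0.95 gives 701.05, rounded up to 702. Both figures reproduce, and nothing about NEWS2 or laboratory values enters them.

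**Variance comparison.** In units of the Day 1 variance, with complete pairs:

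- raw change: 1 + k² − 2k·rho
- Day 1 as covariate: k²(1 − rho²)

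The ratio of the first to the second, minus one, is the extra sample that raw change needs for equal precision. For k = 1 it simplifies to 2(1 − rho)/(1 − rho²) − 1 = 2/(1 + rho) − 1.

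| Assumed rho | k = 1 | k = 1.5 | k = 0.75 |
|---|---|---|---|
| 0.2 | 2/1.2 = 1.67 (+67%) | 2.65/2.16 = 1.23 (+23%) | 1.2625/0.54 = 2.34 (+134%) |
| 0.5 | 2/1.5 = 1.33 (+33%) | 1.75/1.6875 = 1.04 (+4%) | 0.8125/0.4219 = 1.93 (+93%) |
| 0.7 | 2/1.7 = 1.18 (+18%) | 1.00 (about 0%) | 1.79 (+79%) |

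At k = 1 and rho = 0.9 the figure is 2/1.9 − 1 = 5%; at rho = 0 it is 100%. Simulation at N = 666 with k = 1 gave ratios of 1.66 (rho 0.2) and 1.31 (rho 0.5), in line with the formula.

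**The same loss as power.** Take an effect with 85% power under the adjusted model, k = 1. Under raw change its power is Φ(2.996×√((1 + rho)/2) − 1.960): 64% at rho 0.2, 74% at 0.5 and 79% at 0.7.

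**When raw change loses to ignoring baseline.** This requires 1 + k² − 2k·rho > k², that is rho < 1/(2k): below 0.5 at k = 1, below 0.33 at k = 1.5.

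**Change or follow-up as the response.** If follow-up = a + b·treatment + c·Day 1, then change = a + b·treatment + (c − 1)·Day 1. The treatment coefficient b is identical. The wording in Table 2 is therefore compatible with adjustment.

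**The case against.** The strongest reply is that the plan leaves a gap and has not made a wrong choice. Defining an endpoint as change does not fix the model, and the identity above shows that a change endpoint can be analysed with Day 1 as a covariate. The mention of means with confidence intervals is an example of description, and a later SAP is promised. This stands: a reader might infer that the protocol chose raw change over adjustment, and the documents do not support that. It does not remove the point, because Sections 9.4.2 and 9.4.3 hand specific items (missing-data sensitivity analyses) to the SAP, and the NEWS2 and laboratory model is not among them.

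For laboratory values the reply is stronger still. Section 9.4.4 states no between-arm test on laboratory means, and change in the ordinal scale is only summarised by proportions in Section 9.4.3, so change endpoints may be meant as descriptive. The case for a model there rests on Table 2 framing the objective as a comparison with control.

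The size is also open to challenge. Entry requires oxygen by cannula or mask (Section 5.1) and excludes ventilated patients (Section 5.2), which may narrow Day 1 NEWS2 while follow-up spans recovery to ECMO. A larger follow-up SD of this kind can make the loss small. That is fair, and it is why no single percentage belongs in the conclusion.

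Finally, chance baseline imbalance should not be counted as a second harm. Under randomization it is part of the same variance.

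**Conclusion.** The point holds as a free improvement to the stated analysis. Followed literally, the plan compares unadjusted mean changes. A model with the Day 1 value is at least as precise in large samples and uses data already scheduled.

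The size is conditional on the assumed correlation and SD ratio. A reader might take 33–67% as the cost, but that range belongs only to correlations of 0.5 down to 0.2 with equal SDs, and 67% is not an upper bound. Correlation and SD ratio probably differ by day and by laboratory test.

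A reader might also infer that the trial is undersized. It is not on this account: sizing rests on the binary primary endpoint, and that analysis is untouched.

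The variance formula assumes complete pairs and is only indicative here. By Table 2 and Section 8.4.1, NEWS2 and laboratory values before Day 15 come from participants in hospital, and Day 15 and 29 values only from those still in hospital or seen in person. Baseline adjustment does not cure that selection.

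**What to change.** In Sections 9.4.3 and 9.4.4, or in the SAP before unblinding, state that the between-arm difference in NEWS2 and in each laboratory value at each scheduled day will be estimated from a linear model with treatment, the Day 1 value and age stratum (under 65 vs 65 and over). The response may be the follow-up value or the change. Log-transform skewed laboratory values, using the log scale for both Day 1 and follow-up. Report the adjusted difference with its 95% confidence interval and keep raw mean change by arm as a descriptive column. Say alongside it which participants contribute at each day, since the model does not address who is missing.

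The cost is wording only: no new measurement, visit or change to the sample size.
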